4.2.2 Secondary outcome variables

- Mortality rate from all causes at 3 and 12 months
- Mortality rate from respiratory disease at 3 and 12 months
- Mortality rate from cardiovascular disease at 3 and 12 months
- Hospitalization rate from all causes at 3 and 12 months
- Hospitalization rate with a primary diagnosis of respiratory disease or respiratory infection at 3 and 12 months
- Hospitalization rate with a primary diagnosis of cardiovascular disease at 3 and 12 months
- Rate of an incident diagnosis of cardiovascular disease at 3 and 12 months

Self-reported questionnaire data collected at 3 and 12 months:

- Self-rated oxygen utilization
- Breathlessness (Multidimensional Dyspnea Profile; MDP)
- Fatigue (FACIT-Fatigue)
- Informant-rated cognition (IQCODE and FAQ)
- Self-rated cognition (BAS)
- Health-related quality of life (CAT and EQ5D-5L)
- Global impression of change from baseline (GIC)
- Self-reported physical activity
- Preference of continuing treatment

5 Study design

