7.6 Analysis of secondary variables

Hospitalizations are analyzed using Fine Gray regression [ref 1,2,3] accounting for death as competing event. All-cause mortality will be analyzed as the secondary outcome. Number of competing events will be presented for each analysis. Other secondary endpoints are analyzed using two-sided Student's t-tests for continuous variables (including HRQOL, breathlessness, cognition, fatigue, activity, and health care usage) and chi-2 test for categorical variables (causes of death, cognition, treatment preference). Correlational analyses, including of factors predictive of the primary and secondary outcomes will be conducted using linear regression (continuous outcomes), logistic regression (categorical outcomes), and Cox and Fine-Gray regression models (time to event outcomes).

All analyses are subject to underlying conditions – if not fulfilled due to e.g. a too small sample, it will not be attempted. Analyses of secondary variables other than the ones underlined in section 4.2.2 will be performed at Region Blekinge.

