	Median (IQR)		
	Min-Max		
Subgroup 4	n		
	Mean (SD)		
	Median (IQR)		
	Min-Max		

Table 9 Description of outcomes

The table below shows the descriptive data by treatment group for each outcome.

Table 9.1 ITT

	Outcome	Statistics	LTOT 24h/day n	LTOT 15h/day n	Total n
At 3 months	All-cause mortality	n(%)			
	All-cause Hospitalization	n(%)			
	Composite (All-cause mortality/ All-cause Hospitalization)	n(%)			
	Mortality from respiratory disease	n(%)			
	Mortality from cardiovascular disease	n(%)			
	Hospitalization from respiratory disease	n(%)			
	Hospitalization from cardiovascular disease	n(%)			
	Self-reported hours of oxygen* (within 24 hours)	n Mean (SD) Median (IQR) Min-Max			
At 12 months	All-cause mortality	n(%)			
	All-cause Hospitalization	n(%)			
	Composite (All-cause mortality/ All-cause Hospitalization)	n(%)			
	Mortality from respiratory disease	n(%)			
	Mortality from cardiovascular disease	n(%)			
	Hospitalization from respiratory disease	n(%)			
	Hospitalization from cardiovascular disease	n(%)			
	Self-reported hours of oxygen* (within 24 hours)	n Mean (SD) Median (IQR) Min-Max			

* Self-reported oxygen use is defined as mean hours/day. If missing, we will use mean h/day last week, using the questionnaire at 12 months, or (if missing) 3 months.

Table 9.2 PP

Table 9.3 Subgroup 1

Table 9.4 Subgroup 2

Table 9.5 Subgroup 3

Table 9.6 Subgroup 4

Table 10 Analysis of the primary variable

Table 10.1 Primary outcome

Population	Outcome	Reference group	HR (90% CI)	p-value*	p-value**
ITT	Composite event of death or 1 st hospitalization at 1 year	LTOT 15h/day	x.xx (x.xx-x.xx)	x.xx	x.xxx
PP	Composite event of death or 1 st hospitalization at 1 year	LTOT 15h/day	x.xx (x.xx-x.xx)	x.xx	x.xxx

*The p-value for the difference between treatments H0: HR=1

** The p-value corresponds to the one-sided test, at 5% significance level, that the lower limit exceeds the hypothesized value 0.67

Table 10.2 Primary outcome adjusted for sex and age

Similar table as in 10.1 repeated adjusting for sex and age (in years) at randomization. A frailty model will be performed with “center” as a random effect to account for the clustering by hospital.

Table 11 Analyses of secondary variables

Table 11.1 Secondary outcome (ITT)

Population	Outcome	Reference group	n events/competing events	HR (90% CI)	p-value*	p-value**
At 3 months	Composite event of death or 1 st hospitalization	LTOT 15h/day	xx	x.xx (x.xx-x.xx)	x.xx	x.xxx

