	All-cause mortality	LTOT 15h/day	xx	x.xx (x.xx-x.xx)	x.xx	x.xxx
	All-cause Hospitalization***	LTOT 15h/day	xx/xx	x.xx (x.xx-x.xx)	x.xx	x.xxx
	Mortality from respiratory disease	LTOT 15h/day	xx	x.xx (x.xx-x.xx)	x.xx	x.xxx
	Mortality from cardiovascular disease	LTOT 15h/day	xx	x.xx (x.xx-x.xx)	x.xx	x.xxx
	Hospitalization from respiratory disease***	LTOT 15h/day	xx/xx	x.xx (x.xx-x.xx)	x.xx	x.xxx
	Hospitalization from cardiovascular disease***	LTOT 15h/day	xx/xx	x.xx (x.xx-x.xx)	x.xx	x.xxx
At 1 year	All-cause mortality	LTOT 15h/day	xx	x.xx (x.xx-x.xx)	x.xx	x.xxx
	All-cause Hospitalization ***	LTOT 15h/day	xx/xx	x.xx (x.xx-x.xx)	x.xx	x.xxx
	Mortality from respiratory disease	LTOT 15h/day	xx	x.xx (x.xx-x.xx)	x.xx	x.xxx

	Mortality from cardiovascular disease	LTOT 15h/day	xx/xx	x.xx (x.xx-x.xx)	x.xx	x.xxx
	Hospitalization from respiratory disease***	LTOT 15h/day	xx/xx	x.xx (x.xx-x.xx)	x.xx	x.xxx
	Hospitalization from cardiovascular disease***	LTOT 15h/day	xx	x.xx (x.xx-x.xx)	x.xx	x.xxx

*** Hospitalizations are analyzed using Fine Gray regression accounting for death as competing event

Table 11.2 Secondary outcome (PP)

Table 11.3 Secondary outcome (Subgroup 1)

Table 11.4 Secondary outcome (Subgroup 2)

Table 11.5 Secondary outcome (Subgroup 3)

Table 11.6 Secondary outcome (Subgroup 4)

Table 11.7 Analysis of Self-reported hours of oxygen

Similar table as in 10.1

	Population	Outcome	Mean difference (95% CI)	p-value**
At 3 months	ITT	Self-reported hours of oxygen* (within 24 hours)	x.xx (x.xx-x.xx)	x.xx
	PP	Self-reported hours of oxygen* (within 24 hours)	x.xx (x.xx-x.xx)	x.xx
	Subgroup 1	Self-reported hours of oxygen* (within 24 hours)	x.xx (x.xx-x.xx)	x.xx
	Subgroup 2	Self-reported hours of oxygen* (within 24 hours)	x.xx (x.xx-x.xx)	x.xx
	Subgroup 3	Self-reported hours of oxygen* (within 24 hours)	x.xx (x.xx-x.xx)	x.xx
	Subgroup 4	Self-reported hours of oxygen* (within 24 hours)	x.xx (x.xx-x.xx)	x.xx
At 1 year	ITT	Self-reported hours of oxygen* (within 24 hours)	x.xx (x.xx-x.xx)	x.xx
	PP	Self-reported hours of oxygen* (within 24 hours)	x.xx (x.xx-x.xx)	x.xx
	Subgroup 1	Self-reported hours of oxygen* (within 24 hours)	x.xx (x.xx-x.xx)	x.xx
	Subgroup 2	Self-reported hours of oxygen* (within 24 hours)	x.xx (x.xx-x.xx)	x.xx
	Subgroup 3	Self-reported hours of oxygen* (within 24 hours)	x.xx (x.xx-x.xx)	x.xx
	Subgroup 4	Self-reported hours of oxygen* (within 24 hours)	x.xx (x.xx-x.xx)	x.xx

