[figure not shown]
[figure not shown]

Figure 3 Cumulative hazard by treatment

Figure 3.1 Primary outcome (ITT)

[figure not shown]
Similar figures will be constructed for all primary and secondary outcomes (at 3 months and 1 year) presented by ITT, PP, Subgroups 1-4.

Figure 4 Kaplan-Meier figures

Kaplan-Meier figures will also be presented for all primary and secondary outcomes

Figure 5 HR with non-superiority limit for the primary endpoint

90% confidence intervals for HR_{24hvs.15h}, for the ITT, PP and subgroup populations. The p-value corresponds to the one-sided test, at 5% significance level, that the lower limit exceeds the hypothesized value 0.67.

Similar figures will be created for all secondary endpoints

3 Listings

[Listing 1](#) Patient disposition

[Listing 2](#) Demographics and characteristics at screening visit

Participant characteristics should also include center, population and randomized treatment group.

[Listing 3](#) Time of randomization to death or censoring

[Listing 4](#) Patients withdrawal

[Listing 5](#) Patients discontinuing LTOT

[Listing 6](#) Time of randomization to hospitalization or censoring

[Listing 7](#) Subjects excluded from the ITT and PP

[Listing 8](#) Screening failures

[Listing 9](#) Adverse events

[Listing 10](#) Loss to follow-up for the composite endpoint of death or 1st hospitalization

[Listing 11](#) Study termination (End of study)

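### Figure 4 orders Kaplan-Meier curves for hospitalization outcomes in which the SAP treats death as a competing event, so the plotted hospitalization risks would be too high

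*SAP*

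**What the plan says.** In the body of Appendix 2 (Output Shells), Figure 4 carries a single instruction: "Kaplan-Meier figures will also be presented for all primary and secondary outcomes". It makes no exception. (The appendix's contents list gives the number 4 to the hazard ratio figure; the body is meant here.)

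Section 4.2.2 lists three hospitalization outcomes among the secondary outcomes. The first covers every admission: "Hospitalization rate from all causes at 3 and 12 months". The second is limited to one group of diagnoses: "Hospitalization rate with a primary diagnosis of respiratory disease or respiratory infection at 3 and 12 months". The third is limited to another group: "Hospitalization rate with a primary diagnosis of cardiovascular disease at 3 and 12 months".

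For their analysis, section 7.6 states: "Hospitalizations are analyzed using Fine Gray regression [ref 1,2,3] accounting for death as competing event". The footnote to Table 11.1 repeats this: "Hospitalizations are analyzed using Fine Gray regression accounting for death as competing event". Section 7.6 also asks for the number of competing events, and the Table 5.13 shell has a row for it under each hospitalization outcome.

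Table 9.1 gives the number and percentage with each event, by arm, at 3 and 12 months: "The table below shows the descriptive data by treatment group for each outcome". Figure 3 is a cumulative hazard plot. No cumulative incidence plot is specified anywhere.

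**The concern.** The SAP has already decided that death competes with hospitalization, and it models and counts accordingly. Figure 4 does not carry that decision into the graphs. In a Kaplan-Meier curve for time to hospitalization, a patient who dies without admission is ordinarily censored at death. The method then assumes that this patient would have been admitted later at the same rate as those still alive. One minus the curve therefore estimates admission risk in a setting where nobody dies, not the probability of being admitted within a year.

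Two things follow in the study report. If follow-up is otherwise complete, the plotted one-year risk would lie above the percentage in Table 9.1 for the same arm and outcome. And the curve would not show the quantity described by the Fine-Gray hazard ratio in Table 11.1, which is a model for the cumulative incidence. Figure 3 does not fill the gap: with deaths censored, a cumulative hazard is essentially a transformation of the same Kaplan-Meier curve.

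**Working it through.** **Inputs from the SAP**
- One-year probability of death or first hospitalization: 80% (section 9.2).
- Planned size: 230 patients, 1:1, so 115 per arm (section 9.2).
- No loss to follow-up expected for the primary composite in the ITT population (section 9.2).

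**Inputs assumed**
- Constant hazards over the year.
- s, the share of first events that are deaths. The SAP gives no split, so s is varied.
- Deaths censored in the Kaplan-Meier curve; no other censoring before day 365.

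**Step 1. The SAP's own figure.** The sample size formula in section 9.2 uses 0.8 as the overall event probability: n = ((1.645 + 0.842) / ln 1.5)² / (0.25 × 0.8) = 188.03, rounded up to 189. This agrees with the SAP, so 80% is used below as the total one-year risk.

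**Step 2. All-cause hospitalization.** The total hazard is −ln(0.2) = 1.609.
- Cumulative incidence of hospitalization = 0.8 × (1 − s).
- One minus Kaplan-Meier = 1 − exp(−1.609 × (1 − s)) = 1 − 0.2^(1 − s).

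| s (assumed) | Cumulative incidence | 1 − Kaplan-Meier | Excess (points) |
|---|---|---|---|
| 5% | 76.0% | 78.3% | 2.3 |
| 10% | 72.0% | 76.5% | 4.5 |
| 20% | 64.0% | 72.4% | 8.4 |
| 30% | 56.0% | 67.6% | 11.6 |

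A simulation at s = 20% gave a crude proportion hospitalized of 64.1% and one minus Kaplan-Meier of 72.5%, which agrees.

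For scale, the standard error of one arm's cumulative incidence at s = 10% is √(0.72 × 0.28 / 115) = 4.2 points, so the excess is about 1.1 standard errors. At s = 20% it is √(0.64 × 0.36 / 115) = 4.5 points, and the excess is about 1.9 standard errors.

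**Step 3. Cause-specific hospitalization.** Let h be the admission hazard for the cause and μ = −ln(1 − m) the death hazard, with m the one-year mortality (assumed). Cumulative incidence = h / (h + μ) × (1 − exp(−(h + μ))). A Kaplan-Meier risk of 40% (h = 0.511) corresponds to a cumulative incidence of 38.1%, 36.2%, 34.2% and 32.0% at mortality of 10%, 20%, 30% and 40%. A Kaplan-Meier risk of 20% corresponds to 19.0%, 18.0%, 16.9% and 15.8%.

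**Step 4. Contrast between arms.** Suppose 24 h/day had a death hazard ratio of 0.67 and no effect on the admission hazard. The Kaplan-Meier curves would then coincide.
- At s = 10%, the 24 h arm's death hazard is 0.161 × 0.67 = 0.108 and its admission hazard is 1.448. Its cumulative incidence is 1.448 / 1.556 × (1 − exp(−1.556)) = 73.4%, against 72.0%: a difference of 1.4 points.
- At s = 20%, the same calculation gives 66.6% against 64.0%: a difference of 2.6 points.

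The standard error of a difference between two arms is about √2 × 4.2 = 5.9 to √2 × 4.5 = 6.3 points, so this distortion is only about 0.24 to 0.41 standard errors.

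**The case against.** The strongest reply is that nothing inferential depends on this figure. The hospitalization estimates and tests are specified with death competing, the competing events are counted, and Table 9.1 already orders the crude percentages. Figure 4 is an addition to Figure 3. All of this stands, and it limits the point to presentation.

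A second reply is that the SAP does not say how a death enters the hospitalization time. If patients who die were kept in the risk set to day 365, and follow-up were otherwise complete, the product-limit curve would reproduce the cumulative incidence. That is arithmetically right, but it is not what is ordinarily meant by Kaplan-Meier and the SAP does not state it. Nor does the shell say whether the curve or its complement is drawn. If the curve itself is drawn, the hospitalization-free proportion is too low by the same amount.

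A third reply is that the instruction is generic, since taken literally it also covers fatigue and quality of life scores. That supports rewording it, not leaving it.

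A fourth is that a cause-specific display can usefully stand beside a Fine-Gray model. In Step 4 the coinciding curves correctly show no effect on the admission hazard. But Figure 3 already gives that view, and nothing gives the other.

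A reader might go further and infer that Figure 4 flatly contradicts Table 9.1. The SAP does not support so strong a reading. The two agree in wording and would differ only in results, and the percentage in Table 9.1 equals the cumulative incidence only without other censoring. Section 9.2 expects complete follow-up only for the primary composite in the ITT population. Section 7.5 censors some patients who stop oxygen in the primary analysis, and the SAP does not say whether that rule extends to hospitalization. If it does, the table and even a correct cumulative incidence curve would agree only approximately.

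**Conclusion.** The point holds as a display error in secondary endpoints. As worded, Figure 4 applies Kaplan-Meier to three outcomes for which the SAP itself names death as a competing event, and no planned figure shows the cumulative incidence that the Fine-Gray model describes.

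With censoring at death, the direction is certain whenever some patients die before admission and others are admitted later. The size is not fixed by the SAP. For all-cause hospitalization the excess is about 2 to 8 points at one year if 5% to 20% of first events are deaths, given constant hazards and the 80% composite rate.

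It would be wrong to infer that the hospitalization hazard ratios or tests are biased, that the primary analysis is affected, or that the arm comparison is seriously distorted. The first two do not use the figure, and the contrast effect in Step 4 is small against its standard error.

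The same fault applies to Kaplan-Meier curves for respiratory and cardiovascular mortality, where deaths from other causes compete. Kaplan-Meier is appropriate for the composite and for all-cause mortality, where no death competes with the event.

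**What to change.** Reword the Figure 4 shell by outcome:
- **Composite and all-cause mortality:** keep Kaplan-Meier.
- **All-cause, respiratory and cardiovascular hospitalization:** plot the Aalen-Johansen cumulative incidence by arm, with death as the competing event.
- **Respiratory and cardiovascular mortality:** plot the Aalen-Johansen cumulative incidence by arm, with death from other causes as the competing event.

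The cost is a few lines in the shells and a different plotting option in the software already named in section 13. No new data or patients are needed. The only visible consequence is that the plotted risks will be somewhat lower.

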9.1 Limit of non-superiority and Hypotheses

A time-to-composite event survival analysis, with composite event equal to death or 1st hospitalization as endpoint, is used. The hypothesis of non-superiority of continuous oxygen is tested. The null hypothesis is rejected if the hazard ratio (HR) of continuous oxygen vs. 15h/day exceeds the limit 0.67. The use of oxygen is burdensome and with hospitalization, being less serious than death, incorporated into the primary endpoint, the HR of 0.67 was judged to be the appropriate limit for the composite primary outcome. This was the difference in mortality or hospitalization that the investigators judged to be clinically worthwhile. (See also section 10 Changes to the planned analysis.)

$H_0: HR_{24h/day} \leq 0.67$

$H_A: HR_{24h/day} > 0.67$ Continuous oxygen is not better than 15h/day;

If significance is obtained, the conclusion is that LTOT prescribed for 24 h/day does not reduce the rate of the composite event of all-cause death or 1st hospitalization at 1 year compared to LTOT prescribed for 15 h/day in patients starting LTOT for chronic respiratory failure.

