The original design of this trial was based on a time-to-event survival analysis with death as endpoint and the hypothesis of non-superiority of continuous oxygen with a hazard ratio (HR) of 0.83 (larger than this would indicate non-superiority). This was the difference in mortality that the investigators judged to be clinically worthwhile. With the current design, which was specified in amendment 3 (2020-01-22), time-to-composite event survival analysis is used, with composite event equal to death or 1st hospitalization. Since the use of oxygen is burdensome and hospitalization less serious than death, an HR of 0.67 was judged to be appropriate for the composite primary outcome. The recently published large study of LTOT (LOTT) (see protocol reference 13) had an HR of 0.60 in their amendment for the composite endpoint of death or 1st hospitalization and an expansion of the primary analysis population, but that study is for supplemental oxygen vs. none (which should reduce the HR) and patients that were less ill with milder hypoxemia (which should increase the HR) and thus not directly comparable.

Summary of differences as compared to the original protocol

1. A composite event of death or 1st hospitalization, instead of death as the event.
2. A lower limit of non-superiority; 0.67 instead of 0.83.
3. The primary analysis is based on all randomized patients, instead of only the COPD patients.
4. A simplification of the secondary analyses due to the reduction of the sample size.

11 Description of derived variables

The description of derived variables is attached in appendix Draft_SAP_v1.0 (DV).docx.

12 Description of output

The output specification (output shells, OS), describing tables, graphs and lists that will be included in the study report, is attached in appendix Draft_SAP_v1.0 (OS).docx.

13 Statistical software

Statistical analyses will primarily be performed using SAS v. 9.4 or later and/or R (Version 4.2.3).

14 References

- [3] Fine, J. P., and Gray, R. J. (1999). "A Proportional Hazards Model for the Subdistribution of a Competing Risk." *Journal of the American Statistical Association* 94:496–509.

DERIVED VARIABLES

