* Self-reported oxygen use is defined as mean hours/day. If missing, we will use mean h/day last week, using the questionnaire at 12 months, or (if missing) 3 months. (Duration=number of hours per day)

**t-test for mean difference

Table 12 Adverse events (PP and ITT)

Table 12.1 Adverse events

This table will be constructed if there is enough data.

	LTOT 15h/day n=	LTOT 24h/day n=	Total n=
Number of patients with AE (Total number of AE)	n[n]	n[n]	n[n]
Number of patients with SAE (Total number of SAE)	n[n]	n[n]	n[n]
Number of patients with possibly related AE (Number of possibly related AE)	n[n]	n[n]	n[n]
Number of patients with probably related AE (Number of probably related AE)	n[n]	n[n]	n[n]
Number of patients with unrelated AE (Number of unrelated AE)	n[n]	n[n]	n[n]
Number of AE with maximum intensity=MILD	n	n	n
Number of AE with maximum intensity=MODERATE	n	n	n
Number of AE with maximum intensity=SEVERE	n	n	n
Number of patients with maximum AE intensity=MILD	n	n	n
Number of patients with maximum AE intensity=MODERATE	n	n	n
Number of patients with maximum AE intensity=SEVERE	n	n	n

Table 12.2 Time to adverse events

		LTOT 15h/day n=	LTOT 24h/day n=	Total n=
Time to adverse events (all adverse events)	n			
	Mean (SD)			
	Median (IQR)			
	Min-Max			

2 Figures

NOTE: All figures below are based on dummy data

Figure 1 [Figures for inclusion over time](#)

Figure 1.1 Cumulative enrollment over time in the study (all randomized patients)

[figure not shown]

Figure 1.2 Cumulative enrollment over time in the study (by treatment)

If applicable

Figure 1.3 Cumulative enrollment over time in the study (by site)

If applicable

Figure 1.4 Cumulative enrollment over time in the study (by subgroup)

If applicable

Figure 1.5 Histogram with number of included patients by site and by treatment group

[figure not shown]

Figure 1.6 Reasons why the screened patients were not included in the study

[figure not shown]

Figure 1.7 Kaplan-Meier figure: Time from start until the patient stops being treated

A figure will be constructed and presented by treatment arm. Patients who stop being treated with oxygen before one year will be censored at this time.

Figure 2 CONSORT flow chart

* A patient is correctly randomized if he or she fulfills the inclusion criteria but not the exclusion criteria, has signed informed consent and has been randomized in Swedevox within four weeks of starting LTOT.

**All registry data available except for withdrawals

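### The output shells appear to carry the 1-year composite's 0.67 limit over to secondary endpoints for which the SAP states no limit, most seriously to mortality

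*SAP*

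**What the plan says.** Sections 9.1 and 10 of the SAP set and justify the limit. Section 9.1 says that "with hospitalization, being less serious than death, incorporated into the primary endpoint, the HR of 0.67 was judged to be the appropriate limit" and draws its conclusion for the composite at 1 year. Section 10 says that "an HR of 0.67 was judged to be appropriate for the composite primary outcome". It also records that the superseded design, with death as the endpoint, used 0.83. Section 7.5 applies the 0.67 test to the composite at day 365.

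Section 7.6 covers the secondary variables. It names Fine-Gray regression for hospitalizations and mentions all-cause mortality, but states no limit, hypothesis or sidedness for either.

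Appendix 2 (output shells) contains:

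- **Table 10.1** (1-year composite): columns HR (90% CI), `p-value*` and `p-value**`. The single asterisk is the test of HR=1. For the double asterisk: "The p-value corresponds to the one-sided test, at 5% significance level, that the lower limit exceeds the hypothesized value 0.67".
- **Table 11.1** (secondary outcomes): a column "n events/competing events", then the same HR (90% CI), `p-value*` and `p-value**` columns for the 3-month composite and for every mortality and hospitalization row. The only footnote belongs to the triple asterisk: "Hospitalizations are analyzed using Fine Gray regression accounting for death as competing event".
- **Table 11.7** (self-reported oxygen hours): the double asterisk means "t-test for mean difference".
- **Figure 5** (listed as Figure 4 in the contents): titled "HR with non-superiority limit for the primary endpoint", with 90% intervals and the same one-sided 0.67 test, followed by "Similar figures will be created for all secondary endpoints".
- **Tables 5.13-5.24**: HR with 95% CI and one p-value for the composite, all-cause mortality, both cause-specific mortalities and both cause-specific hospitalizations, at 3 and 12 months. All-cause hospitalization has no HR line there.

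**The concern.** A programmer who follows the shells has to fill two p-value columns in Table 11.1 without being told which tests they hold. The only definition of a double asterisk attached to a hazard ratio is the 0.67 test under Table 10.1, and the 90% interval is the usual companion of a one-sided 5% test. The likely output is a one-sided p-value against 0.67 in every mortality and hospitalization row, and a figure with a line at 0.67 for each.

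The secondary objectives in section 4.1.2 ask whether 24 h/day fails to reduce each rate. A small `p-value**` in the mortality row would look like a yes, although it would rule out only reductions in hazard of 33% or more (1 - 0.67 = 0.33). Nothing in the SAP says that a smaller mortality reduction is not worthwhile. In addition, the same HR could appear with a 95% interval in Table 5 and a 90% interval in Table 11, with no explanation.

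**Working it through.** **1. The plan's own figure.** Section 9.2 uses one-sided alpha 0.05, 80% power, null HR 1.5 (the inverse of about 0.67), true HR 1, event probability 0.8 and 1:1 allocation:

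n = (1.645 + 0.842)² / [0.25 × 0.8 × (ln 1.5)²] = 188.03, so 189.

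This matches the SAP. The sample size for the composite is not in dispute.

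**2. Does the reason for 0.67 carry over?**

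| Row in the shells | Limit stated in SAP text | Does the stated reason apply? |
|---|---|---|
| Composite at 1 year (Table 10.1, Figure 5) | 0.67 (7.5, 9.1, 10) | Yes |
| Composite at 3 months (Table 11.1) | None | Same endpoint, but the limit and conclusion are stated for 1 year |
| All-cause and cause-specific mortality | None | The argument that hospitalization is less serious than death cannot apply |
| Hospitalization (Fine-Gray) | None | The severity argument could apply, but 0.67 was set for a Cox HR of the composite, not a subdistribution HR |

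Mortality is the strong case. The hospitalization and 3-month rows are weaker ones: they lack a limit, but the stated reasons do not rule one out.

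**3. What a pass at 0.67 would mean for mortality.** The inputs are N = 230 with 1:1 allocation and one-sided alpha 0.05 (section 9.2). The SAP gives no death rate, so 20% to 50% is assumed, which is 46 to 115 deaths. With d events, SE(ln HR) ≈ 2/√d.

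- Smallest observed HR that passes = 0.67 × exp(1.645 × 2/√d).
- Probability of passing at a true HR h = Φ[(ln h − ln 0.67) × √d/2 − 1.645].

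Worked for d = 92: 0.67 × exp(3.29/9.592) = 0.67 × exp(0.343) = 0.944. The 95% interval at that value is 0.944 × exp(±1.96 × 0.2085) = 0.63 to 1.42.

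| Deaths (assumed) | Smallest passing HR | 95% CI at that HR | P(pass), true HR 0.75 | P(pass), true HR 1 |
|---|---|---|---|---|
| 46 | 1.09 | 0.61-1.94 | 10% | 39% |
| 68 | 1.00 (0.998) | 0.62-1.61 | 12% | 50% |
| 92 | 0.94 | 0.63-1.42 | 13% (0.135) | 61% |
| 115 | 0.91 | 0.63-1.31 | 15% | 69% |

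The smallest passing HR equals 1 at d = (2 × 1.645 / ln(1/0.67))² = 67.5. An observed HR below 1 can therefore pass only from 68 deaths upward. For a cause-specific mortality with 20 events the observed HR would have to reach 1.40, so a misleading pass is unlikely there.

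**4. Hospitalization.** Assume 115 to 184 first hospitalizations. The upper figure is 0.8 × 230, the composite event count, and so a ceiling. Using the same SE as an approximation for the Fine-Gray rows, the smallest passing HR is 0.91 to 0.85.

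**5. Sensitivity to the limit, as history only.** Against the superseded 0.83, the smallest passing HR would be 1.35, 1.17 and 1.13 at 46, 92 and 115 deaths. What the mortality row appears to show therefore depends on which limit is used, and the current SAP states none for it.

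**The case against.** **The use of 0.67 is inferred.** No sentence in the SAP applies it to a secondary endpoint, and the title of Figure 5 restricts the limit to the primary one. Repeating the figure for all secondary endpoints cannot be literal, since self-reported oxygen hours has no HR, so the instruction may concern layout only. The 3-month composite gives Table 11.1 a possible innocent reason for its `p-value**` column. This stands, and the point is therefore only that the shells appear to apply the limit. A reader might cite the mention of table 11 in section 7.5 as proof, but that may refer to the 3-month composite row alone.

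**Tables 5.13-5.24 already plan 95% intervals and a p-value without 0.67 for most of these HRs.** This is true and reduces the risk of misreading. It also shows that the shells hold two interval levels for the same quantities.

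**Section 9.1 gives a second reason, the burden of oxygen, which applies to mortality too.** This is fair, but the SAP does not say that burden alone supports 0.67 for death.

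**Passing at a true HR of 0.75 is a correct rejection of HR ≤ 0.67, not an error.** This also stands. The figures show how little a pass would say about mortality; they are not an inflated error rate.

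**A two-sided test of HR=1 could mislead as well**, because a non-significant result invites the reading that treatment fails to reduce the rate. The fix has to address this.

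A reader might also infer that 0.83 is the mortality limit in force and that the SAP contradicts itself. It does not: 0.83 belongs to the superseded design.

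**Conclusion.** The point holds as a defect in the secondary outputs that should be corrected. It is certain that both asterisks are undefined in Table 11.1, that Figure 5 is extended with no limit named for the other endpoints, and that section 7.6 gives none. It is inferred, on good grounds, that following the shells would test mortality and hospitalization against 0.67. For mortality the stated justification then fails. Under the assumed 92 deaths, an observed HR of 0.944 with a 95% interval of 0.63 to 1.42 would just pass.

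It would be too strong to say that the SAP plans a formal non-superiority claim on mortality. It attaches no conclusion to these rows, and each row also shows the HR and its interval. The figures rest on assumed event counts and on the 2/√d approximation, which was not checked for the Fine-Gray rows. The primary analysis, its alpha and the sample size are untouched.

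**What to change.** - State in section 7.6, under Table 11.1 and under Figure 5 that the 0.67 limit and its one-sided p-value apply only to the composite at 1 year (Table 10 and Figure 5).
- For every Table 11.1 row, including the 3-month composite, report the HR (labelled as a subdistribution HR for hospitalization) with a 95% interval, consistent with Tables 5.13-5.24, and the two-sided p-value for HR=1. Define the single asterisk accordingly and remove the `p-value**` column. Carry this through Tables 11.2-11.6.
- Limit the analogues of Figure 5 to time-to-event endpoints, with 95% intervals and no 0.67 line or one-sided test.
- Add that a non-significant two-sided p-value is not evidence that 24 h/day fails to reduce the rate.
- If a non-superiority statement is wanted for a secondary endpoint, give that endpoint its own limit and reason before unblinding.

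The cost is a few sentences and footnotes, one column dropped from Table 11 and one reference line removed from the secondary figures. The downside is that no formal non-superiority claim can be made on secondary endpoints unless a limit is added for them.
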